3.1 Overall Design

The overall goals are to refine and demonstrate the feasibility of implementing the Oncolo-GIST intervention, determine its acceptability to oncologists, and potential for improving advanced cancer patients' prognostic understanding. In pursuing these goals, this study aims to determine the promise of the Oncolo-GIST approach for affecting the targeted outcomes and given positive results, to position us for a larger RCT. We, thus, propose to examine key aspects of intervention development, to evaluate the NIH's Stage I activities of the Stage Model of Behavioral Therapies (e.g., intervention refinement, adaptation, and pilot testing),^{12 13} and to explore Oncolo-GIST's preliminary efficacy.

Both qualitative and quantitative methods will be used in Phase 1. During the Phase 1 interviews (Aim #1) we will obtain feedback from relevant stakeholders/key informants (bereaved caregivers and clinicians) on an early draft of the Oncolo-GIST manual and proposed approach using a version of the Delphi method¹⁴ in which we interview bereaved family caregivers of advanced cancer patients (n=10) and oncology clinicians who care for patients with advanced gastrointestinal (GI) and thoracic (lung) cancers (n=10). The participants will have the option of completing a recorded phone interview or answering identical questions via a link to REDCap. Participants will also be asked demographic and oncology based communication questions specific to either clinicians or caregivers.

In Phase 2, for the pilot cluster RCT study (Aim #3), we will recruit adult patients (n=50) with metastatic GI, head and neck, or lung cancers with scan results that reveal progression (worsened disease) on an initial systemic treatment; that is, patients whose life-expectancy can reliably be estimated to be months, not years.^{5 9} Medical oncologists (n=4) who care for these patients will also be consented for study participation and half (n=2) will be randomized to receive the brief "Oncolo-GIST communication" training. The Oncolo-GIST training will provide instruction in how to introduce the topic of prognosis, describe scan results as "worse," prognosis as "likely months, not years," and expected treatment outcomes (e.g., "not expected to be cured by treatment," and expected impact on quality of life – that is, whether the anticancer treatment is likely to make them feel overall better or worse). We expect 12-13 patients will be clustered within each of the 4 oncologists. Hierarchical Linear Modeling (HLM) techniques will be employed to address the non-independence of patient assessments within each cluster. Patients (n=25) will be seen by either an Oncolo-GIST trained oncologist or an oncologist not trained in the intervention; that is, usual care (n=25). Patients in both arms will have met the same eligibility criteria (i.e., have similar prognoses).

Thus, we will get initial feedback on the Oncolo-GIST intervention from relevant stakeholders and key informants, obtain information on the patient and oncologist experience with the intervention and evaluate its feasibility and acceptability. Finally, we will obtain preliminary effect size estimates

on the Oncolo-GIST Version 2.0's effect on our primary outcome – patient prognostic understanding – to inform the planning of a future larger scale efficacy randomized controlled trial (RCT). Patients will be assessed by trained research staff in the week prior to a scheduled meeting with their oncologist to discuss the scan results. This will provide patients' baseline levels of prognostic understanding and enable us to determine how the intervention relates to pre-post scan visit changes in prognostic understanding. Although the first scheduled scan after study enrollment may not reveal progressive disease, we have been assured by Drs. [name] and [name] that only exceptional cancer patients will not progress within 12 months of baseline. We thus propose to follow patients for 12 months or until a progression is detected in the scan, whichever comes first.

Patients will be assessed pre-scan, post-scan within a week of that progressive scan visit and after their two next scans, if applicable. [see Human Subjects section for Study Timeline & Assessment Schedule and details of assessment procedures]. Although not all patients are expected to die within the study observation period, given a median life expectancy of ~4-5 months from baseline,⁹ we expect nearly half of the enrolled patients will die 4 months from baseline, and that the vast majority will die during the study observation period. Thus, for all patients enrolled in this study, the medical care that they receive can reasonably be considered end-of-life care, whether they die during the study observation period or not.

Informed consent of participants will occur in-person or will be conducted remotely by sending the participants the consent form by mail or secure file transfer (transfer.weill.cornell.edu) or via a REDCap Informed Consent form (see attached) The REDCap form will be implemented in the following manner to ensure informed consent: a research assistant will send the form to a participant prior to a scheduled phone call, go through the consent with the participant over the phone, and answer any questions. The participant will need to type the correct name of the person who recruited them in the REDCap form: a wrong answer will be counted as "not consented." REDCap has been automatically set up with the e-consent framework to auto-archive consents and email a PDF copy of the signed form to the participant. A research assistant will then call the participants to go over consent and answer any questions they may have prior to any assessments. Participants will keep one copy of the consent form and send one copy back by mail or secure file transfer prior to any assessments/data collection.

Phase 2 documents will be submitted upon completion of the Phase 1 Interviews and the Phase 1 Open Trial respectively. No participants will be enrolled without IRB approval of these documents.

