4.2 Inclusion Criteria

Phase 1 Interviews:

Bereaved Caregivers:

1. Caregivers of patients who died in the past year with a primary diagnoses of GI or lung cancer
2. Fluent in English

Clinicians:

1. Currently care for patients with metastatic GI and lung cancers as an oncologist, palliative care physician, nurse, nurse practitioner, social worker, or psychologist

Phase 2:

Patients:

1. Male or female \geq 18 years of age.
2. Receiving ongoing care (\geq 2 visits) that includes regular scans
3. Progression on at least 1 line of systemic cancer therapy
4. Prognosis from an oncologist of less than 12 months
5. Receiving care from an oncologist participating in the Oncolo-GIST study
6. Fluent in English

Clinicians:

1. Specialize in Lung, Head and Neck, and GI cancers
2. Currently provide care at the WCM Lung, Head and Neck, and GI cancer clinics
3. Fluent in English

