4.3 Exclusion Criteria

Phase 1 Interviews:

Bereaved Caregivers:

1. Caregivers of patients who died longer than 1 year from the time of enrollment
2. Caregivers of a patient that did not have a primary diagnoses of GI or lung cancer
3. Not fluent in English

Clinicians:

1. Does not currently care for patients with metastatic GI and lung cancers as either an oncologist, palliative care physician, nurse, nurse practitioner, social worker, or psychologist

Phase 2:

Patients:

1. Under 18 years of age
2. Not receiving ongoing cancer care (≥ 2 visits) that includes regular scans
3. Not progressing on at least 1 line of systemic cancer therapy
1. Prognosis from an oncologists of 12 months or more
4. Not receiving care from an oncologist participating in the Oncolo-GIST study
5. Not fluent in English
6. Cognitive impairment, as indicated by a score of <8 on the Short Portable Mental Status Questionnaire or a diagnosis of dementia or a related condition

Clinicians:

1. Does not specialize in Lung, Head and Neck, and GI cancers
2. Does not currently provide care at the WCM Lung, Head and Neck, and GI cancer clinics
3. Not fluent in English

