4.4 Strategies for Recruitment and Retention

Phase 1 Interviews: Clinicians and bereaved caregivers will be recruited by targeted sampling. We will use WCM's EPIC system as well request referrals from Weill Cornell Medicine (WCM) clinicians to recruit 10 bereaved caregivers of GI and lung cancer patients who died within the past year.

Trained research co-investigators will screen deceased patients using EPIC after referral. If deemed eligible, caregivers will be contacted by either phone or email by non-clinician co-investigators.

Oncology clinicians including oncologists, palliative care physicians, nurses, nurse practitioners, social workers, and psychologists who care for patients with GI and lung cancer, will be identified for recruitment via convenience and snowball sampling by either phone or email. These clinicians are known by co-investigators and/or their affiliates. Recruitment emails will include an attached flyer. Flyers will also be distributed on WCM/NYP properties. Phone recruitment will be by script and will include information from the flyer. Participants will not be contacted more than twice if there is no response and if at any point, a potential participant asks not to be contacted, study staff members will thank them for their time, and be put on a do not contact list. Participants will receive \$100 compensation via a ClinCard after the interview is completed.

Phase 2: Patients will be identified from weekly reviews of patient charts and discussions with the WCM GI, Head and Neck, and lung clinic staff working alongside [name] and [name], respectively. Trained research assistants (RA) will screen patients at the Lung and GI Clinics for eligibility, using WCM's EPIC system. If deemed eligible (see eligibility and exclusion criteria), the research assistant will approach the patient in clinic, to explain the study, and the study procedures. Flyers will also be distributed on WCM/NYP properties. Patient subjects will receive \$25 compensation via ClinCard after each interview is completed, with a possible total of \$100 by the

end of the study.

- *Anticipated accrual rate*
 - Phase 1 Interviews
 - Recruit and enroll 10 oncology clinicians and 10 bereaved in the 1st 6 months of the study
 - Phase 2
 - Recruit and enroll 50 patients (3/month for ~ 18 months)

5. Registration Procedures

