6.1 Schedule of Assessments

Table 1. Schedule of trial events for Phase 1 Interviews (Bereaved Caregivers and Clinicians)

	Pre-study	Visit 1 (Interview)
Screening	X	
Informed Consent (see note)	X	
Review of Oncolo-GIST intervention		X
Demographics		X
Oncology Based Communication Questions		X
Semi-structured Interview		X

Table 2. Schedule of trial events for Phase 2

	Arm	Pre-Study	Pre-Scan	Post-Scan 1 (approx. 1 week)	Post-Scan 2	Post-Scan 3	Post-Scan 4 (up to 12 months)
Short Portable Mental Status Questionnaire ^s	P	X					
Health Literacy Assessment (REALM) ^s	P	X					
Informed Consent	B	X					
Oncolo-GIST Training (Clinicians)	C*	X					
Demographics	P		X				
4 Item Illness Understanding	P		X				
Treatment Intent	P		X				
Treatment Preferences	P		X				
CWC II Psychological questions	P		X				
NCCN Distress Thermometer	P		X				
The Human Connection Scale	P		X	X	X	X	
HADS	P		X	X	X	X	
McGill Quality of Life Questionnaire	P		X	X	X	X	
PSWQ-Ultra Brief	P		X				
PANAS	P		X				
Primary Appraisal Secondary Appraisal (PASA) items (Threat and Challenge subscales only)	P		X				
Post Scan Clinician Questionnaire	C			X			
Medical Chart Abstraction	C				X	X	X
Post Scan Patient Questionnaire	P			X	X	X	
Training Quiz	C*	X					
Post-Study Questionnaire	C						X

C = Clinicians, P = Patients, B = Both, ^s= Screening, * = Intervention Arm Only

Note: The Post-Scan 4 Chart Abstraction will occur when monitoring if progression of the disease is found after Post-Scan 3 or the patient is deceased; up to 12 months.

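### The pre-scan baseline is taken after oncologists are randomised and trained, so a pre-post change, and to a lesser degree a baseline-adjusted difference, may understate the effect if the method was already in use

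*Combined protocol and SAP*

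**What the plan says.** **Timing of baseline.** Section 3.1: "Patients will be assessed by trained research staff in the week prior to a scheduled meeting with their oncologist to discuss the scan results". The same section treats this score as baseline and says it will give patients' "baseline levels of prognostic understanding and enable us to determine how the intervention relates to pre-post scan visit changes" in prognostic understanding.

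**Timing of training.** In Table 2 of section 6.1, the row beginning "Oncolo-GIST Training (Clinicians" is marked under Pre-Study. The row "4 Item Illness Understanding" is marked under Pre-Scan, the next column. No calendar date is given for training.

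**Who enters.** Section 4.2 requires "Progression on at least 1 line of systemic cancer therapy" and "Receiving care from an oncologist participating in the Oncolo-GIST study". Section 4.3 excludes patients "Not receiving ongoing cancer care (≥ 2 visits) that includes regular scans". Section 4.4 plans to enrol 50 patients at about 3 a month over roughly 18 months.

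**What training covers.** Section 3.1 describes general instruction on raising prognosis, on wording for worsened scans and life expectancy, and on expected treatment outcomes. It does not confine use to the visit after the pre-scan interview. Table 2 has no measure of what the oncologist said before Post-Scan 1.

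**Analysis.** Section 8.3.1 specifies a hierarchical linear model with oncologist as a random effect and baseline covariates, with health literacy as the only example. It does not say whether the outcome is the post-scan score or a change, or whether the pre-scan score is a covariate.

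**The concern.** A baseline is useful for measuring change when treatment cannot have touched it. Here the treatment is attached to the oncologist, who is randomised and trained before patients give their pre-scan score. The qualifying progression is the kind of event the training addresses. If the discussion of that progression took place after training and with the study oncologist, some of the benefit may already be in the intervention arm's pre-scan score.

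Subtracting that score removes the early benefit. Change then estimates only the further gain at the study visit, while the post-scan difference estimates the whole effect of having a trained oncologist. The pilot exists to supply a preliminary effect size for a larger trial, so an attenuated estimate would carry straight into that trial's planning.

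**Working it through.** **Reference figure.** Section 8.1 states power above 80% at d = 0.8 and 30% at d = 0.5, with 48 patients and 4 oncologists. With 24 per arm, two-sided alpha 0.05 (assumed, since none is stated), a normal test and no clustering, I obtain 79.1% and 41.0%. The stated pair is not reproduced. That is a separate matter, and the present point does not rest on it.

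**Inputs.** The true effect d = 0.8 SD is the large effect in section 8.1. Two inputs are not in the documents and are shown as ranges:

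- f, the average share of the effect already present in the intervention arm's pre-scan score
- r, the pre-post correlation (equal pre and post SDs are assumed)

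**Formulas.** The pre-scan difference between arms is f·d and the post-scan difference is d.

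- Post-scan difference: d
- Change: d − f·d = d(1 − f)
- Post-scan adjusted for pre-scan: d − r·f·d = d(1 − r·f)

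**Estimated effect (SD units), d = 0.8**

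| f | Change | Adjusted, r = 0.3 | Adjusted, r = 0.5 | Adjusted, r = 0.7 | Post-scan only |
|---|---|---|---|---|---|
| 0 | 0.80 | 0.80 | 0.80 | 0.80 | 0.80 |
| 0.10 | 0.72 | 0.776 | 0.76 | 0.744 | 0.80 |
| 0.25 | 0.60 | 0.74 | 0.70 | 0.66 | 0.80 |
| 0.50 | 0.40 | 0.68 | 0.60 | 0.52 | 0.80 |

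At r = 0.5 adjustment loses half of what change loses: at f = 0.25, 0.10 against 0.20.

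**Power at r = 0.5** (24 per arm, two-sided 0.05, normal test, no clustering). The residual SD is √(2(1 − r)) = 1 for change and √(1 − r²) = 0.866 for adjustment.

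| f | Change | Adjusted | Post-scan only |
|---|---|---|---|
| 0 | 79% | 89% | 79% |
| 0.10 | 70% | 86% | 79% |
| 0.25 | 55% | 80% | 79% |
| 0.50 | 28% | 67% | 79% |

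These figures only compare the three measures. Clustering within four oncologists lowers all of them.

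**Could f exceed zero?** Suppose training falls at the start of accrual, enrolment is uniform over 18 months, and the qualifying progression was discussed with the study oncologist L months before enrolment. The share of intervention patients whose discussion followed training is (18 − L)/18: 83% at L = 3, 67% at L = 6 and 33% at L = 12. L is not in the documents. This is a share of patients possibly exposed, not a value of f.

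**Would the data show it?** The pre-scan difference would be 0.25 × 0.8 = 0.2 SD or 0.5 × 0.8 = 0.4 SD. Its standard error without clustering is √(2/24) = 0.289 SD, so these are 0.7 and 1.4 standard errors. A raised baseline could be seen, but could not be told apart from chance or from differences between the oncologists' panels.

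**The case against.** Three stronger readings are tempting, and the documents do not support them.

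- **That the pre-post change does understate the effect.** This needs f above zero. No passage dates the training, says that the qualifying visits followed it, or says that they were with the study oncologist. Early enrollees' visits could all precede training. If f = 0 there is no bias.
- **That a change score is the planned primary analysis.** Pre-post change appears in one sentence of section 3.1. The primary objective in section 1 concerns understanding after the prognosis discussion, section 8.1 powers on the score itself, and section 8.3.1 names no change score. An analysis of the post-scan score without pre-scan adjustment would be unaffected.
- **That contamination would be invisible.** The four items are collected pre-scan in both arms, so a raised intervention-arm baseline would be visible, though ambiguous with four oncologists.

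The pre-scan score also has real value. With two oncologists per arm, panels may differ in tumour type and prior understanding, and adjustment helps to control this where an unadjusted post-scan comparison does not. Power need not suffer either: at f = 0.25 and r = 0.5 the adjusted analysis has 80%, against 79% unadjusted.

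All of this stands, and it limits the point to a possible attenuation of unknown size. It does not remove the point. Section 3.1 names change, section 8.3.1 does not settle the measure, and nothing planned records exposure before baseline.

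**Conclusion.** The point holds as a conditional one. The pre-scan score is post-randomisation and follows training, and the plan neither prevents nor records earlier use of the method. If such use raised understanding before the interview, a pre-post change is attenuated by (1 − f) and a baseline-adjusted difference by (1 − r·f). A post-scan comparison is not attenuated by this mechanism. For a true 0.8 SD, f from 0.10 to 0.50 gives 0.72 to 0.40 for change, and 0.76 to 0.60 for adjustment at r = 0.5. These sizes are illustrations resting on assumed f and r and on equal SDs. No single corrected figure can be derived from the documents.

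Adjustment is preferable to change whatever f is: it loses less if f is positive and is more precise if f is zero.

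**What to change.** **In section 8.3.1:**

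- Define the primary effect as the between-arm difference in the Post-Scan 1 prognostic-understanding score from the hierarchical model, adjusted for the pre-scan score. Do not use pre-post change as the effect measure, and align the sentence in section 3.1.
- Prespecify the Post-Scan 1 difference without pre-scan adjustment as a sensitivity analysis. State that it is free of this attenuation but does not control panel differences among only four oncologists.
- Report pre-scan scores by arm.

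**In data collection:** record each oncologist's training date (randomisation date for usual care) and, for each patient, the number of visits with the study oncologist between that date and the pre-scan interview. Section 3.2 says the abstracted data will be deleted at study completion, so derive this count before then.

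**Leave out** an effect estimate by none versus any prior visit, or report it descriptively only. Unexposed patients would mostly be early enrollees, so the split is confounded with calendar time, and about 25 patients per arm in four clusters is too few.

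**Cost:** one date per oncologist, one extra field from charts already being abstracted, one sensitivity analysis and a few sentences of text. No extra patients or interviews are needed. The remaining drawback is that the adjusted primary can still be attenuated if f is above zero, which is why the unadjusted result should be reported beside it.

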3.2 Interviews, Focus Groups, Surveys, and/or Observations

A. Administration

▪ Timing and Frequency

Phase 1 Interviews: Clinicians and bereaved caregivers will complete a one-time, 2 hour phone study session or REDCap survey (including embedded intervention manual) link.

Phase 2: Patients will be assessed in the week prior to their scheduled scan, within 1 week of the clinic visit in which progressive scan results are discussed, and then after their next two scans, if they have them, to explore intervention effects on primary and secondary outcomes, respectively. Oncologists will be assessed in the week following that same clinic visit to obtain their impressions of the discussion of prognosis and the patient's prognostic understanding. All these assessments will take 20-30 minutes.

Trained oncologists will complete a brief (5-minute) post-training quiz, and all oncologists will complete a brief (5-minute) survey on Oncolo-GIST at the end of the

study. Additionally, patients will be monitored via EPIC for progression of disease up to 12 months.

- *Location*

Phase 1 interviews of caregivers and clinicians will take place at a location convenient to the participant over the phone or via REDCap. Assessments of patients and clinicians in the pilot stage will take place in-person in clinic, at a time convenient for the participant at a different appointment, or over the telephone. Patients in Phase 2 will also have the option of completing the surveys themselves via a secure web link if this is more convenient to them.

- *Person Identifiers*

Co-investigators may review EPIC to identify potential participants who meet eligibility. Contact information and appointment information will also be collected for either in-person or letter (postal and email) recruitment. Only data from potential participants will be stored on secure servers. Patient subjects will also have data collected via medical chart abstraction including diagnoses, medications, advanced directives, and types of care received (e.g. hospice). These data will be deleted upon completion of the study.

B. Study Instruments

- Phase 1 Interviews for both clinician and bereaved caregiver subjects will consist of a survey including demographics and oncology based communication questions specific to either the clinicians or caregivers. After each section of the Oncolo-GIST manual, participants will answer open-ended questions about the module they just reviewed.
- Phase 2 patients will be screened with a mental status questionnaire and health literacy assessment. At the first visit they will answer an assessment battery including but not limited to questions about treatment and mental status prior to discussing their scan results. After the scan results, patients will answer questions to assess prognostic understanding and treatment preferences at 3 post-scan time points (1 week after initial scan, one week after second scan, one week after third scan from enrollment)). Trained co-investigators will also collect data via medical chart abstraction. Clinicians (Phase 2) will answer an initial demographic survey and surveys including prognosis questions, patient understanding, and patient medical status for each patient participant. Clinicians trained in Oncolo-GIST will also complete a short post-training quiz to assess their understanding of the Oncolo-GIST manual. All clinicians will complete a brief study completion questionnaire to assess the feasibility and acceptability of the Oncolo-GIST method.

- Referral information

Data collected/received from participants will be reviewed within 24-48 hours and research study staff will be responsible for addressing elevated psychological symptoms/suicidality identified on the assessments so that timely and appropriate psychiatric assessment and care can be provided. If a participant at acute risk of self-harm or harm to others cannot be reached by the study team within 3 hours (after at least two phone call attempts and an email requesting a call back), the participant's emergency contact(s) will be contacted.

4. Study Design

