10.1.1 Unanticipated Problem Reporting

Not applicable

11. Safety Stopping Rules

We would stop the study if patients in the intervention arm became psychologically distressed and their distress was attributable to the way we are training oncologists to communicate, though it is our hypothesis and aim to demonstrate the emotional and cognitive benefits of our approach. Psychological distress is here defined as self-reported distress on the part of the subject or distress as evaluated by the researcher (defined as an AE in section 7.2.6). As we administer multiple psychometric assessments per interview and enquire about the patient's wellbeing, there is ample opportunity to catch and discuss psychological distress.

References

¹ Beauchamp, Tom L.; Childress, James F. (1994). *Principles of Biomedical Ethics* (Fourth ed.). New York: Oxford University Press. ISBN 0-19-508536-1.

² Elsayyad, Ahmed. "Informed Consent for Comparative Effectiveness Trials". *New England Journal of Medicine*. 370: 1958–1960. doi:10.1056/NEJMc1403310.

³ WHO | Informed Consent Form Templates". who.int. Retrieved 14 September 2014

⁴ [name] AS, Prigerson HG, O'Reilly EM, Maciejewski PK. Discussions of Life Expectancy and Changes in Illness Understanding in Patients with Advanced Cancer. *J Clin Oncol*. 2016 Jul 10;34(20):2398-403. doi: 10.1200/JCO.2015.63.6696. Epub 2016 May 23. PubMed PMID: 27217454; PubMed Central PMCID: PMC4981977

⁵ Lambden J, Zhang B, Friedlander R, Prigerson HG. Accuracy of Oncologists' Life-Expectancy Estimates Recalled by Their Advanced Cancer Patients: Correlates and Outcomes. *J Palliat Med*. 2016 Dec;19(12):1296- 1303. Epub 2016 Aug 30. PubMed PMID: 27574869; PubMed Central PMCID: PMC5144872.

⁶ Mack JW, Weeks JC, Wright AA, Block SD, Prigerson HG. End-of-life discussions, goal attainment, and distress at the end of life: predictors and outcomes of receipt of care consistent with preferences. *J Clin*

Oncol. 2010 Mar 1;28(7):1203-8. doi: 10.1200/JCO.2009.25.4672. Epub 2010 Feb 1. PubMed PMID:20124172; PubMed Central PMCID: PMC2834470.

⁷ Wright AA, Zhang B, Ray A, Mack JW, Trice E, Balboni T, Mitchell SL, Jackson VA, Block SD, Maciejewski PK, Prigerson HG. Associations between end-of-life discussions, patient mental health, medical care near death, and caregiver bereavement adjustment. *JAMA*. 2008 Oct 8;300(14):1665-73.
doi:10.1001/jama.300.14.1665. PubMed PMID: 18840840; PubMed Central PMCID:PMC2853806.

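### A Phase 2 web survey indicating acute self-harm risk could go unread for up to 48 hours before the 3-hour contact step can begin, and no faster route is described.

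*Combined protocol and SAP*

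**What the plan says.** Four places in the protocol bear on this.

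- **Section 3.2 B, Referral information.** "Data collected/received from participants will be reviewed within 24-48 hours". The review window is not limited to any mode of completion. The duty to act on raised symptoms or suicidality found in the assessments falls to the research staff, and the stated aim is that psychiatric care be timely. For a participant at acute risk, the emergency contact is called if that person "cannot be reached by the study team within 3 hours"; two or more calls and an email must have been tried. The event that starts the 3 hours is not named.
- **Section 3.2 A, Location.** The staff-attended routes are in person in clinic, at another appointment, or by telephone. In addition, "Patients in Phase 2 will also have the option of completing the surveys themselves via a secure web link".
- **Section 7.3.6, Data Safety and Monitoring Plan.** Responses are to be monitored for severe distress, with no time limit, mode or alert given. There is no medical monitor, and reports to the DSMC are annual.
- **Section 11, Safety Stopping Rules.** Because several psychometric measures are given at each interview, the section says "there is ample opportunity to catch and discuss psychological distress". Distress counts if the subject reports it or the researcher judges it present.

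**The concern.** The plan treats acute risk of self-harm as something to act on within hours once it is known, but the data that would reveal it may stay unread for one to two days. In an interview, a staff member is at least present when the answer is given. On the web route no one is, so the review is the first moment at which staff can learn of the risk.

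The assurance in Section 11 depends on distress being noticed and talked through during an interview. That does not carry over to a survey completed alone, where the researcher's own judgement of distress is also unavailable at that assessment.

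The stakes are patient safety. Eligible patients have a prognosis of less than 12 months, and the first post-scan survey falls within a week of the visit at which progression is discussed. Section 9.1 names psychological distress as the only potential adverse event, so detecting it is the trial's main safety task. The review in Section 3.2 B is the only detection step with a time attached.

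**Working it through.** The plan gives no figure for time to escalation, so there is none to reproduce. The check is a timeline sum and a count.

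**Inputs**
- Review window: 24 to 48 h, all modes (Section 3.2 B).
- Contact window before the emergency contact is called: 3 h, start undefined (Section 3.2 B).
- Unattended web completion: allowed for Phase 2 patients (Section 3.2 A).
- Phase 2 patients: 50 (Section 8.1).
- Patient survey points: pre-scan and post-scan 1, 2 and 3, so 4 (Section 6.1, Table 2). The payment of $25 per interview up to $100 in Section 4.4 agrees: 100 / 25 = 4.

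**Time to emergency contact**

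Time = delay until the risk is identified + 3 h, for a patient who then cannot be reached.

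- Web survey read at the outer limit: 48 + 3 = 51 h.
- Web survey read at 24 h: 24 + 3 = 27 h.

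This takes the 3 h to run from review. The protocol does not say so, but no one can start calling about a response that has not been read.

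**Difference between web and interview**

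The documents do not say how quickly an interviewer escalates, so two cases bound it.

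- Risk recognised live in the interview (assumption): identification delay 0 h. The web route is then later by up to 24 h if read at 24 h (24 - 0), or up to 48 h at the outer limit (48 - 0).
- Interview data handled only under the general review window: identification delay up to 48 h in both modes, so the difference is 48 - 48 = 0 h.

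The range under the text as written is 0 to 48 h. In the second case the modes do not differ, but the 51 h limit then applies to every mode.

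**Exposure**

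Ceiling = 50 x 4 = 200 surveys. The real number will be lower. The last two assessments take place only if the patient has further scans, Section 3.1 expects nearly half of patients to die within 4 months of baseline, and the share choosing the web link is not stated.

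**The case against.** The best defence is that the two limits do not conflict. One is an interval for reading incoming data; the other is a rule for a participant already known to be at risk who does not answer. They run in sequence, and both can be followed. That is correct. A reader might infer that the two limits cannot apply to the same event, but the text does not support that. What remains is that their sum is long for a response no one witnesses, and that the start of the second interval is undefined.

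Other stronger readings also fail.

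- **Web patients are escalated two days later than interviewed patients.** No on-the-spot rule for interviews is stated and the review window covers every mode, so this is the upper end of a 0 to 48 h range.
- **The delay is a large multiple of the interview delay.** Dividing 51 by 3 is tempting, but the 3 hours apply to someone who cannot be reached. A patient speaking to an interviewer has been reached, so 3 hours is not the interview figure and the ratio has no meaning.
- **Adverse event counts are biased between arms.** That would require web use to differ by arm, which nothing in the documents indicates. Self-report and assessment scores exist on both routes, and late reading mainly changes when such an event is logged.

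Two further objections limit the point without removing it. Table 2 names no dedicated self-harm instrument, and the psychological questions and Distress Thermometer are scheduled pre-scan only, so it is not shown that every web survey asks about suicidality. The referral paragraph nevertheless expects suicidality to be found on the assessments. Section 3.1 also points to a Human Subjects section for assessment details; it is not part of the documents reviewed and might describe an alert.

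**Conclusion.** The point holds as a gap in the safety procedure. Following the protocol as written, a web response indicating acute risk could go unread for up to 48 hours, giving up to about 51 hours to the emergency contact (27 if read at 24 hours). At most 200 surveys are exposed.

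This rests on three assumptions: the 3 hours cannot start before the response is read, no alert is described in a document not reviewed here, and the survey contains an item that can reveal the risk. Sample size, power and type I error are unaffected. The change is worth making because it is cheap and the review is the only timed safeguard.

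**What to change.** - Reconcile Sections 3.2 A, 3.2 B, 7.3.6 and 11. State how acute risk is detected in a survey completed without staff present, what event starts the 3-hour window, and whether the review window also governs interview answers. The time limits themselves are for the investigators to set.
- Configure REDCap, already the study's data system, to notify the staff already responsible for referral whenever a web response meets the study's own flag for elevated symptoms or suicidality. If the flag is not yet defined item by item, define it.
- Record the completion mode and the time from submission to review for each survey, so that the delay can be reported.

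The cost is some REDCap configuration, a short clarification in the protocol and two extra data fields. The downsides are some false alerts, and that the investigators must decide how alerts arriving outside working hours are handled, which may need staff cover.
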